## 7 SAMPLE SIZE JUSTIFICATION

Sample size is not based on a power analysis. Sample size reflects the exploratory nature of this study.

Approximately 95 subjects are planned for enrollment in the Main study with 40 and 55 subjects randomized to the low epoetin alfa dose group and the high epoetin alfa dose group, respectively. Approximately 30 subjects are planned for enrollment in the ESA hyporesponder parallel study.

Enrollment may be increased by up to approximately 20 additional subjects in the Main study and by up to approximately 30 additional subjects in the ESA hyporesponder parallel study to ensure adequate data are captured for the primary, PK/PD, and safety endpoints.

## 8 STUDY ANALYSES

### 8.1 General Consideration

The following rules will be adopted when summarizing the data:

1. The Main Study and the ESA Hyporesponder Parallel Study will be summarized separately, but in an analogous manner, for all endpoints.
  - a. For the Main study, the low epoetin dose group ( $\leq 90$  U/kg/week), 450 mg of vadadustat, 300 mg of vadadustat and epoetin will be displayed side by side. In addition, the total vadadustat will be presented as well.
  - b. For the Main study, the high epoetin dose group ( $> 90$  and  $< 300$  U/kg/week), 600 mg, 450 mg, 300 mg of vadadustat and epoetin will be displayed side by side. In addition, the total vadadustat will be presented as well.
  - c. For the Main study, a summary of total vadadustat vs. epoetin will be presented as well. For the background information, a total column for all randomized patients will be presented except certain PK/PD parameters.
  - d. For the ESA Hyporesponder Parallel Study ( $\geq 300$  U/kg/week), 600 mg and epoetin will be displayed side by side.
2. For efficacy data analysis, 3 tables will be presented for some selected efficacy endpoints:
  - a. Overall summary by week including the first weeks and post Week 12 by treatment group which is based on the randomized dose group.
  - b. For subjects who switched Vadadustat dosing from QD to TIW dosing.
  - c. For subjects who did not switch from QD to TIW dosing after Week 12.
3. For safety data analysis, 5 sets of tables will be presented for some selected safety parameters:
  - a. Overall summary for all weeks including the first 12 weeks and post Week 12 by treatment group
  - b. Overall summary for the first 12 weeks of treatment.
  - c. Overall summary for Weeks 12 to the end of study for both switched and not switched patients at Week 12
  - d. Overall summary for Weeks 12 to the end of study for switched patients
  - e. Overall summary for Weeks 12 to the end of study for not switched patients
4. For patients who switched Vadadustat dosing from QD to TIW dosing at week 12, and then switched back to QD, if there are less than or equal to 20 subjects, only patient

---

listings/profiles will be created. If there are more than 20 patients, summary tables will be created by treatment groups for efficacy and safety.

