**Figure 1: Overview of Study Design**

### **3.1 Screening Period (up to 28 days; Day -28 to Baseline/Day 1)**

For all subjects (Main study and ESA hyporesponder parallel study), the Screening Period starts at the time the informed consent is signed and will be a maximum of 28 days in duration. Baseline/Day 1 will be performed within 28 days of the start of Screening. Subjects who meet all eligibility criteria will be randomized to a vadadustat treatment arm or an epoetin alfa treatment arm. Subjects will be required to stop epoetin alfa treatment for a minimum duration of 5 days before Baseline/Day 1 in the Main study and for a minimum of 2 days before Baseline/Day 1 in the ESA hyporesponder parallel study. In the Main study, randomization will be stratified by the mean weekly epoetin dose calculated over a period of 8 weeks prior to Screening Visit 2 (SV2):

- Low epoetin alfa dose group ( $\leq 90$  U/kg/week)
- High epoetin alfa dose group ( $>90$  to  $<300$  U/kg/week)

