### **3.3 Vadadustat Treatment**

#### Subjects in the Main study randomized to vadadustat:

- Subjects in the low epoetin alfa dose group will start vadadustat at an initial, randomly allocated dose of 300 or 450 mg daily.
- Subjects in the high epoetin alfa dose group will start vadadustat at an initial, randomly allocated dose of 300, 450, or 600 mg daily.

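### The pooled Main-study vadadustat and epoetin columns take no account of the stratification factor, and differ in stratum mix unless both strata use the same vadadustat:epoetin ratio

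*SAP*

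**What the plan says.** SAP section 3.1 says that in the Main study "randomization will be stratified by the mean weekly epoetin dose", with a low and a high group. Section 3.3 gives low-group subjects on vadadustat an "initial, randomly allocated dose of 300 or 450 mg daily" and high-group subjects an "initial, randomly allocated dose of 300, 450, or 600 mg daily". Each stratum also has an epoetin arm. Section 7 plans about 95 Main-study subjects, with "40 and 55 subjects randomized to the low epoetin alfa dose group and the high epoetin alfa dose group, respectively".

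Section 8.1, item 1 governs the tables for all endpoints. Items 1a and 1b show each stratum separately: every vadadustat starting dose, a vadadustat total for that stratum, and that stratum's epoetin arm. Item 1c then adds: "For the Main study, a summary of total vadadustat vs. epoetin will be presented as well". It mentions no stratum weighting. Section 9 keeps the efficacy analysis descriptive and excludes inferential modelling. The SAP states no vadadustat:epoetin ratio and no number per arm.

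**The concern.** The primary objective in section 2.1.1 is daily vadadustat compared with epoetin alfa, and item 1c is the only display that brings the whole Main study together on that question. A reader will compare its two columns directly.

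That comparison is clean only if the strata are mixed in the same proportion in both columns. With two vadadustat arms against one epoetin arm in the low stratum, and three against one in the high stratum, the proportions match only if arm sizes were chosen to make them match. If they were not, the vadadustat column holds relatively more subjects with high prior epoetin need. Part of any difference between strata in Hb change, target-range attainment, rescue, transfusion or adverse events would then appear as a difference between treatments. A larger sample would not remove this, and the pooled table alone would not reveal it.

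**Working it through.** **Inputs from the SAP.** Low stratum 40 subjects, high stratum 55 (section 7); 40 + 55 = 95, which agrees with the stated total. Vadadustat arms: two in the low stratum, three in the high (section 3.3). One epoetin arm in each (section 8.1, items 1a and 1b).

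**Assumptions, not in the SAP.** The allocation ratio, the between-stratum difference in outcome, and the SD of Hb change.

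**Formula.** Let pV and pE be the high-stratum shares of the pooled vadadustat and epoetin columns, d a treatment difference common to both strata, and g the high-minus-low difference in mean outcome. The raw pooled difference is then d + (pV − pE) × g, and the second term is the distortion.

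**Stratum mix under different allocations.**

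- *Equal arms within each stratum.* Low: 40/3 = 13.33 per arm, so vadadustat 26.67 and epoetin 13.33 (2:1). High: 55/4 = 13.75 per arm, so vadadustat 41.25 and epoetin 13.75 (3:1). pV = 41.25/67.92 = 60.7%; pE = 13.75/27.08 = 50.8%; gap 10.0 points from unrounded shares.
- *One vadadustat arm size a and one epoetin arm size b across both strata.* 2a + b = 40 and 3a + b = 55 give only a = 15, b = 10. The ratios are 30:10 (3:1) and 45:10 (4.5:1). pV = 45/75 = 60%; pE = 10/20 = 50%; gap 10 points.
- *One ratio in both strata.* Both shares equal 55/95 = 57.9%, so the gap is zero. With exact totals of 40 and 55, whole numbers and equal vadadustat arms within a stratum, this needs a/20 = 3c/55, where a and c are the low and high vadadustat arm sizes. So a = 12c/11, and the only solution is c = 11, a = 12: arms of 12/12/16 and 11/11/11/22, a 3:2 ratio.
- *Equal arms with the optional 20 extra subjects.* All in the low stratum: 50.8% vs 40.7%, gap 10.0 points. All in the high stratum: 67.8% vs 58.4%, gap 9.4 points.

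**Size of the distortion at a gap of 0.10.**

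| Assumed stratum difference | Distortion in pooled contrast |
|---|---|
| 0.25 g/dL | 0.025 g/dL |
| 0.5 g/dL | 0.05 g/dL |
| 1.0 g/dL | 0.10 g/dL |
| 20 percentage points | 2 points |
| 40 percentage points | 4 points |

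**For scale.** With 75 vs 20 subjects, the standard error of a mean difference is SD × √(1/75 + 1/20) = SD × 0.2517. For an assumed SD of 0.8 to 1.2 g/dL that is 0.20 to 0.30 g/dL.

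**Precision of the weighted difference in the same layout.** With weights 40/95 and 55/95, the variance is SD² × [(40/95)² × (1/30 + 1/10) + (55/95)² × (1/45 + 1/10)] = SD² × 0.0646, so the standard error is SD × 0.2542, about 1% larger than for the raw pool. Mantel-Haenszel weights are 30 × 10/40 = 7.5 and 45 × 10/55 = 8.18; the standard error is SD × √(1/15.68) = SD × 0.2525, about 0.3% larger.

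**The case against.** The strongest reply is that nothing is shown to be confounded. A different number of arms does not confound by itself. The vadadustat:epoetin ratio must differ between strata, and the outcome must differ by stratum. The SAP states no ratio, allocation is commonly left to the protocol, and the approximate totals of 40 and 55 do not rule out a common ratio. This stands, and the point is conditional for that reason.

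Item 1c is also an addition. Items 1a and 1b already compare vadadustat with epoetin inside each stratum, free of this problem. No test or decision rule rests on the pooled summary, and the plan is deliberately descriptive. This stands too, and it limits the weight of the point.

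The stratum differences used above are assumptions. All arms are titrated to the same 10.0 to 11.0 g/dL range, so a difference of 1.0 g/dL in mean change would span that whole range. The distortion is below the assumed standard error in every case shown. This is correct for Hb; rescue, transfusion and adverse events are not themselves titration targets.

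The reply does not explain why a summary of a stratified trial should drop the stratifier when keeping it needs no model. The two simplest readings of the planned totals both give a 10-point gap.

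**Conclusion.** The point holds conditionally. Item 1c pools across the stratification factor without accounting for it. Unless both strata share one vadadustat:epoetin ratio, the pooled columns differ in high-stratum share by about 10 points, and about one tenth of any true stratum difference is read as a treatment difference. For Hb that is 0.025 to 0.10 g/dL under the assumed stratum differences, against an assumed standard error of 0.20 to 0.30 g/dL. Imbalance is the likelier reading of 40 and 55, but it is not proven.

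A reader might infer that the pooled comparison is confounded as a matter of fact, or that its columns cannot be compared. The SAP does not support either, because a common ratio would make the distortion zero. A reader might also infer that prior epoetin dose was chosen as stratifier because it predicts response; section 3.1 gives no reason for the choice.

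**What to change.** In section 8.1, item 1c, add to the pooled summaries of Hb change, target range, rescue, transfusion and key adverse events a descriptive vadadustat-minus-epoetin difference. Compute it within the low and high strata, then combine the two with weights fixed in advance: each stratum's share of randomized Main-study subjects, or Mantel-Haenszel weights nV × nE/(nV + nE). Keep the raw pooled columns, with a footnote that gives the stratum mix of each column and refers to the tables under items 1a and 1b. Stating the vadadustat:epoetin ratio per stratum in the SAP would let a reader see at once whether the issue arises.

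A confidence interval is optional. A weighted average of two differences is compatible with the descriptive plan in section 9. The cost is SAP wording and one line per pooled table, with a slight loss of precision: about 1% or less in the standard error for the layout worked above. No new data are needed.

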## 8.2 Analysis Population

The following analysis populations will be used in this study:

- Randomized population: defined as all randomized subjects. Analyses of this population will be based on the randomized treatment.
- Full Analysis Population (FAS): all subjects in the randomized population who received at least one dose of study drug and had at least one Hb assessment during the primary efficacy evaluation period. Analyses of this population will be based on the randomized treatment.
- Safety Population: all subjects in the randomized population who received at least one dose of study treatment. Analysis of this population will be based on the actual treatment received. Subjects who received in error some vadadustat and some epoetin alfa will be classified by the more frequently received drug.
- Per protocol (PP) population: all randomized subjects who received study drug during the primary evaluation period, had at least one Hb assessment during the primary efficacy evaluation period, received no rescue therapy (with ESA or transfusion) prior to the evaluation period, and had no major protocol deviation affecting the primary endpoint analyses. Major protocol deviations leading to exclusion from the PP population will be specified prior to database lock on a blinded basis and recorded in a separate document. Analyses of this population will be based on actual treatment received.
- Pharmacokinetic (PK) population: will include all randomized subjects who received study medication (vadadustat or EPO) and had enough drug concentrations to estimate AUC and Cmax. Analysis of this population will be based on the dose amount taken at the date of PK sampling for vadadustat group.

Efficacy analyses will utilize the Randomized, FAS, and PP Populations while safety analyses will utilize the Safety Population. PK analyses will utilize the PK Population. However, if the population size of FAS and PP is  $\geq 95\%$  of the size of randomized population, no additional summary table will be presented for FAS and PP populations.

---

## 8.3 Disposition of Subjects

The number and percentage of subjects randomized and included in each analysis population will be summarized by treatment and overall. Reasons for excluding subjects from the analysis populations will be presented in a by-subject listing.

---

The number of randomized subjects who completed the study period for QD period, switched to TIW period, completed TIW period, switched dosing from TIW back to QD, completed study, discontinued early from study drug, completed or discontinued from the study, and reasons for discontinuation will be summarized by treatment group and overall. For dose changes including dose increase, decrease for different reasons and “dose not changed” will be described in [section 8.9](#).

#### **8.4 Protocol Deviations**

Deviations from the protocol including violations of inclusion/exclusion criteria will be assessed as “minor” or “major” in cooperation with Akebia. Major deviation will be categorized and summarized in table. A data listing of protocol deviations will be provided.

#### **8.5 Demographics and Baseline Characteristics**

Continuous demographic variables, such as age, weight, BMI, and height, will be summarized for the Randomized population, FAS, PP, and Safety using descriptive statistics (n, mean, median, SD, minimum, and maximum value). Categorical demographic variables, such as age category, race, ethnicity, and gender, will be summarized as a proportion of the Randomized population, FAS, PP, and Safety populations.

Ethnic group, race, gender, and age will be included in the demographics and baseline characteristics table. Age will be calculated as using function floor of (informed consent date – birth date + 1)/365.25.

#### **8.6 Baseline Laboratory Data**

Baseline laboratory including hematology, chemistry, folate, vitamin B12, iron indices (serum iron, ferritin, transferrin, TIBC, TSAT) and biomarkers (VEGF and hepcidin) will be summarized for each treatment group based on the safety population.

#### **8.7 Medical History**

Medical history terms including renal and cardiovascular History will be coded using the Medical Dictionary for Regulatory Activities (MedDRA) version 23. and the number and percent of subjects with medical history will be summarized by (SOC) and Preferred Term (PT) for each treatment group based on the safety population.

Etiology of CKD, smoking status, and New York Heart Association Class (NYHA) of cardiovascular history will be summarized for each treatment group for safety population.

In addition, the history of dialysis, CKD diagnosis duration in years will be summarized for each treatment group based on the safety population.

## 8.8 Prior and Concomitant Medication

Prior and concomitant medications will be coded using World Health Organization Drug Dictionary (WHO DD; Sep 2018) and summarized for each treatment group based on the safety population. Prior medication is defined as any medication taken prior to the first dose of the study medication in the initial treatment period. Any medication taken from the day of first dose of the study treatment up to the day of last date of the same study drug date + 4 weeks will be considered as concomitant medication for the treatment analysis.

## 8.9 Study Medication Exposure and Compliance

Study medication exposure and compliance will be summarized using descriptive statistics for the FAS and Safety Population. Study medication and subject dosing diary data will also be presented in data listings.

The calculated compliance rate for a given time period will be derived from exposure data as the number of days on dosing period collected on electronic case report forms (eCRFs) divided by the number of days in that time period.

Compliance will be summarized as follows:

- Descriptive statistics will be summarized by treatment group for entire treatment period.
- Percent compliance will be categorized according to the following categories for entire treatment period for safety population by treatment group:
  - less than 50% (significant drug noncompliance)
  - at least 50%, less than 80% (moderate drug noncompliance)
  - greater or equal 80% (drug compliance)
  - unknown

Study medication exposure and compliance will be summarized for the first 12 weeks, Weeks 12 – 20, and entire treatment period for each treatment group. In addition, for Weeks 12 – 20, patients who switched from daily vadadustat dose to TIW and patients who did not switch at Week 12 will be summarized separately.

For epoetin alfa group, increases in dose relative to last dose will be characterized in the following categories by percentage increase: <50%,  $\geq 50\%$  and <100%, and  $\geq 100\%$ . Subjects will be presented by their maximum category of increase for the first 12 weeks, Weeks 12 – 20, and entire treatment period.

Dose change information including the following categories will be summarized for the first 12 weeks and Weeks 12 – 20 treatment period for each treatment group:

- Dose not changed
- Protocol guided dose reduction
- Dose increased based on Hb assessment
- Dose decreased based on Hb assessment

---

- Dose interrupted based on Hb assessment
- Dose decreased due to adverse event
- Dose interrupted due to adverse event
- Dose restarted
- Transitioned from QD to TIW dosing
- Converted back from TIW to QD dosing

---

## 9 EFFICACY ANALYSIS

The primary efficacy endpoint as well as all other secondary endpoints will be summarized using descriptive statistics by treatment group, as well as by study visit and/or analysis period (the first 12 weeks and Weeks 12 – 20) as appropriate. The ESA hyporesponder parallel study will be analyzed separately from the main study. Mean values of Hb as well as selected other efficacy parameters will be plotted across study visits/periods by treatment group. No adjustment for multiplicity is being used in this exploratory study.

Primary efficacy endpoint will be analyzed and presented for Randomized population, FAS and PP Population. Key secondary efficacy endpoints will be analyzed for Randomized population and PP Population. The rest of efficacy endpoints will be analyzed for Randomized population. No inferential statistical modeling will be used for the efficacy analysis. All efficacy endpoints related to Hb, the observed data will be used for the analysis tables. In addition, a sensitivity analysis of LOCF to impute the missing Hb data will be performed for summary of change from baseline in Hb based on Randomized population.

### 9.1 Primary Endpoint

Mean change in Hb between Baseline (average pretreatment Hb) and the primary evaluation period (average Hb from Weeks 10 to 12). Baseline value is defined as the average of the final two Hb values prior to start of dosing on day 1.

Observed baseline, post-baseline values, and change from baseline values will be presented in descriptive statistics summary by treatment group, as well as by study visit and/or analysis period as appropriate. Mean values of Hb as well as selected other efficacy parameters will be plotted across study visits/periods by treatment group.

### 9.2 Secondary Endpoints

Similarly, all secondary endpoints will be summarized using descriptive statistics. For continuous variables, observed values at specified time points and changes between specified time points will be presented in descriptive statistics summary by treatment group, as well as by study visit and/or analysis period as appropriate. Counts of subjects satisfying stated criteria will be summarized analogously, using descriptive statistics for categorical variables.

- Proportion of subjects with Hb values within the target range (10.0 to 11.0 g/dL, inclusive) at the primary evaluation period (Weeks 10 to 12) for each treatment group
- For subjects who transitioned to TIW vadadustat dosing, mean change in Hb from primary evaluation period (average Hb from Weeks 10 to 12) to the secondary evaluation period (average Hb from Weeks 18 to 20) for each vadadustat dosing group

---

- Mean change in Hb between Baseline (average pretreatment Hb) and the secondary evaluation period (average Hb from Weeks 18 to 20) for each treatment group
- Proportion of subjects with Hb values within the target range (10.0 to 11.0 g/dL, inclusive) at the secondary evaluation period (Weeks 18 to 20) for each treatment group
- For subjects who transitioned to TIW vadadustat dosing, proportion of subjects with Hb values within the target range (10.0 to 11.0 g/dL, inclusive) at the secondary evaluation period (Weeks 18 to 20) for each vadadustat dosing group
- Proportion of subjects with a mean increase in Hb from Baseline to the primary evaluation period  $\geq 0.5$  g/dL (average Hb from Weeks 10 to 12) or with Hb values within the target range (10.0 to 11.0 g/dL, inclusive) at the primary evaluation period (Weeks 10 to 12) for each treatment group
- Proportion of subjects with a mean increase in Hb from Baseline to the secondary evaluation period  $\geq 0.5$  g/dL (average Hb from Weeks 18 to 20) or with Hb values within the target range (10.0 to 11.0 g/dL, inclusive) at the secondary evaluation period (Weeks 18 to 20) for each treatment group

### 9.3 Other Secondary Endpoints

- Intravenous (IV) iron supplementation and oral iron

The average weekly elemental iron use during the treatment period which is defined as first dose date to last dose date + 7 days will be calculated for weekly intervals from both oral and IV iron medications (Oral iron dose will be converted to elemental iron dose; the list will come from the medical team.). The treatment period will be divided in periods of 7 days and for each of these periods the weekly mean of IV iron will be used using the following formula:

$$\text{Weekly iron use for each subject} = \text{Total iron in mg} / [(\text{last dose date} + 7 - \text{first dose date} + 1) / 7]$$

The average weekly iron use will be summarized by treatment group using descriptive statistics. The content of elemental iron for different kinds of IV iron is presented in [Appendix 5](#).

In addition, numbers and percentages of subjects with at least one administration of elemental iron will be summarized by treatment group.

- ESA administration and RBC transfusion

ESA medication will be considered as rescue if the ESA medication was taken between the first dose date to the last dose date + 7 days and the reasons for the ESA medication use is checked as confirmed Hb  $< 8.5$  g/dL on the CRF and the ESA medication wasn't taken during the period of Eurofins ransomware attack (after Jun 20, 2019 and before July 9, 2019).

---

Epoetin alfa dose will be administered based on the subject's central laboratory Hb value and the approved epoetin alfa US PI for adult patients with CKD on dialysis. From Baseline/Day 1 to Week 20, dose will be adjusted to achieve and maintain Hb levels within the target range of 10.0 and 11.0 g/dL, inclusive. Because epoetin alfa is titratable, increase in dose is not considered rescue unless the investigator specifically designates it as such; however, increases in dose relative to last dose will be characterized in three categories by percentage increase: <50%, ≥50% and <100%, and ≥100%. In addition to the investigator's judgement of rescue, the increase in dose ≥50% or ≥100% will be considered as additional conditions for ESA rescue in EPO group.

RBC transfusion will be considered as rescue if the RBC transfusion was taken between the first dose date to the last dose date + 7 days and the reasons for the RBC transfusion is checked as Worsening Anemia due to CKD on the CRF.

[figure not shown]
The study will consider the following efficacy endpoints related to ESA administration and RBC transfusion.

- Receipt of any ESA administration
- Receipt of any ESA administration or dose with at least 50% increase for the EPO group
- Receipt of any ESA administration or dose with at least 100% increase for the EPO group
- Receipt of ESA administration as rescue
- Receipt of ESA administration as rescue or dose with at least 50% increase for the EPO group
- Receipt of ESA administration as rescue or dose with at least 100% increase for the EPO group
- Receipt of any RBC transfusion
- Receipt of RBC transfusion as rescue

Number of subjects received ESA administration (any or rescue) and RBC transfusion (any or rescue) will be summarized by treatment group and time period. The following time periods will be summarizing:

- Baseline visit (inclusive) to week 12 (inclusive)
- Week 12 (exclusive) to week 20 (inclusive)
- Baseline visit (inclusive) to week 20 (inclusive)

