### 5.3 Other Secondary Efficacy Endpoints

- Mean change in Hb between Baseline (average pretreatment Hb) and the secondary evaluation period (average Hb from Weeks 18 to 20)
- Proportion of subjects with Hb values within the target range (10.0 to 11.0 g/dL, inclusive) at the secondary evaluation period (Weeks 18 to 20)
- For subjects who transitioned to TIW vadadustat dosing, proportion of subjects with Hb values within the target range (10.0 to 11.0 g/dL, inclusive) at the secondary evaluation period (Weeks 18 to 20)
- Proportion of subjects with a mean increase in Hb from Baseline to the primary evaluation period  $\geq 0.5$  g/dL (average Hb from Weeks 10 to 12) or with Hb values within the target range (10.0 to 11.0 g/dL, inclusive) at the primary evaluation period (Weeks 10 to 12)
- Proportion of subjects with a mean increase in Hb from Baseline to the secondary evaluation period  $\geq 0.5$  g/dL (average Hb from Weeks 18 to 20) or with Hb values within the target range (10.0 to 11.0 g/dL, inclusive) at the secondary evaluation period (Weeks 18 to 20)
- Intravenous (IV) iron supplementation
- ESA rescue
- RBC transfusion

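### SAP Section 9.3 contradicts itself and Section 5.3 on whether the iron endpoint is IV iron alone or oral plus IV iron

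*SAP*

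**What the plan says.** Section 5.3 names the endpoint in one line: "Intravenous (IV) iron supplementation". Section 9.3 opens the matching item with a wider title, "Intravenous (IV) iron supplementation and oral iron". It then makes these statements:

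- Average weekly elemental iron use "will be calculated for weekly intervals from both oral and IV iron medications".
- On scale: "Oral iron dose will be converted to elemental iron dose; the list will come from the medical team".
- Treatment is cut into 7-day periods, and "for each of these periods the weekly mean of IV iron will be used using the following formula".
- The formula divides "Total iron in mg" by the length of the treatment period in weeks. That period runs from the first dose to seven days after the last dose. No route is attached to the numerator.
- On content: "The content of elemental iron for different kinds of IV iron is presented in" Appendix 5, which covers IV products only.
- The companion count is that "numbers and percentages of subjects with at least one administration of elemental iron will be summarized by treatment group". No route is given here either.

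**The concern.** The text supports two different numerators for one table. The item title, the sentence on both routes, the oral conversion and the undivided total point to oral plus IV iron. The sentence introducing the formula points to IV iron only. Two programmers working from this final plan could produce different results, and each could cite Section 9.3.

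The pooled reading has more of the text behind it, but it does not measure what Section 5.3 lists. A combined elemental total mixes two routes with no stated weighting. A difference between arms in that total could come from oral iron use alone. The oral conversion list is also not fixed in this document, whereas the IV contents are. The efficacy analysis is descriptive only (Section 9), so the summary table is the entire result for this endpoint.

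**Working it through.** The plan gives no iron-use figure to reproduce. The check has two parts: the statements set side by side, and an illustration of what the choice of numerator could do.

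**Which numerator?**

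| Place | Points to |
|---|---|
| Section 5.3, endpoint list | IV only |
| Section 9.3, item title | IV and oral |
| Section 9.3, first sentence | IV and oral |
| Section 9.3, sentence introducing the formula | IV only |
| Section 9.3, formula numerator | route not stated |
| Section 9.3, count of subjects | route not stated |
| Appendix 5 | IV products only |

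No statement reconciles these, and no separate IV-only mean, median or count is unambiguously specified.

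**How much could it matter under pooling?**

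Inputs from the plan:
- 40 low-dose-group and 55 high-dose-group subjects in the Main study (Section 7).
- Three displayed arms in the low group, four in the high group, and a display of total vadadustat against epoetin (Section 8.1).

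Assumptions, none of them in the plan:
- Equal allocation within each group.
- Oral iron of 65 to 195 mg elemental per day, taken throughout the period, with 25 mg/day as a low case.
- Mean IV use of 25 to 100 mg/week.

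Group sizes:
- Single arm: 40/3 = 13.3 or 55/4 = 13.75, taken as 14.
- Epoetin in total: 13.3 + 13.75 = about 27.
- Vadadustat in total: 40 × 2/3 + 55 × 3/4 = 26.7 + 41.25 = about 68.

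The shift in a group mean from one oral user is daily dose × 7 / n. The weekly amounts are 25 × 7 = 175, 65 × 7 = 455 and 195 × 7 = 1365 mg.

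| Group | n | 25 mg/day | 65 mg/day | 195 mg/day |
|---|---|---|---|---|
| Single arm | 14 | 12.5 | 32.5 | 97.5 |
| Total epoetin | 27 | 6.5 | 17 | 50 |
| Total vadadustat | 68 | 2.6 | 7 | 20 |

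(mg/week added to the mean)

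For 65 to 195 mg/day, relative to the assumed IV mean:
- In an arm of 14, the shift runs from 32.5/100 = 33% to 97.5/25 = 390%.
- In total vadadustat, it runs from 7/100 = 7% to 20/25 = 80%.

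Suppose the IV difference, vadadustat minus epoetin, is −20 mg/week. One oral user in a 14-subject vadadustat arm changes it to −20 + 12.5 = −7.5 at 25 mg/day, or to −20 + 32.5 = +12.5 at 65 mg/day. In the total vadadustat comparison, the same user at 65 mg/day gives −20 + 7 = −13, and at 195 mg/day about zero.

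**The 7-day wording.** The text speaks of a mean for each 7-day period, but the formula gives one value per subject. The mean of consecutive weekly totals equals the overall total divided by the number of weeks, apart from a partial last week. With the first dose on Day 1 and the last on Day 141, the formula gives (141 + 7 − 1 + 1)/7 = 21.14 weeks. The numerical effect is therefore negligible.

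**The case against.** A reader might infer that the plan definitely adds oral and IV iron milligram for milligram, and that a few oral users would swamp the IV comparison. The documents do not support that. The sentence introducing the formula names IV iron, Appendix 5 covers IV products only, and equal weighting of the routes is inferred from the elemental conversion and the single total, not written. The size of any distortion depends on oral doses, oral-use rates and mean IV use, none of which the plan states.

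Other points on this side also stand. The planned comparison of total vadadustat with epoetin dilutes one oral user far more than a single arm of 14 does. Section 6 requires the median, minimum and maximum beside the mean, and one to three oral users in 14 would move the median little. No test or decision rule uses this result, and the study is declared exploratory. Section 1 places table specifications in a separate document, so route-specific rows may exist there.

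It can also be said that the item title in Section 9.3 openly extends the endpoint to oral iron. That discloses an extension, but it does not supply an IV-only analysis or remove the conflict with the sentence introducing the formula. A median of pooled iron is likewise still not a median of IV iron.

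**Conclusion.** The contradiction is in the text and needs no assumption: Section 9.3 gives two incompatible descriptions of the numerator, and Section 5.3 agrees with only one of them. The count of users is equally unspecific. As written, the listed IV iron endpoint has no unambiguous analysis.

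The consequence is conditional. If the pooled version is programmed, the table reports something other than IV iron use, and means in the small arms could shift by an amount comparable with IV use itself. The figures illustrate this under assumed oral doses and equal allocation; they do not predict what the trial will show. The effect is weaker at low oral doses and in the larger combined groups. This is a correction that should be made to a secondary endpoint. It does not affect the primary endpoint.

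**What to change.** In Section 9.3:

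- For the Section 5.3 endpoint, make the formula's numerator total IV elemental iron in mg.
- Report oral elemental iron separately, with its own weekly summary.
- Give the number and percentage of subjects with at least one administration by route: IV, oral, and either.
- Label any oral-plus-IV total as supplementary.
- As a minor wording correction, align the 7-day-period sentence with the formula's single whole-treatment value per subject.

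The cost is a few sentences in the SAP and a few table rows. Section 9.3 already treats oral and IV products differently when converting to elemental iron, so it presupposes that route is known for each record. No information is lost, because the combined total can still be shown.
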